### 15.3 Safety Run-In Phase

There is no previous experience with SBRT used concurrently with Nelfinavir in this study population. Therefore, to ensure that the combination is safe, the first six patients will be treated and observed for toxicity for 30 days after radiation before continuing with further accrual. 6 patients will be enrolled at the proposed dose of Nelfinavir and SBRT. If  $\leq 2$  toxicity events occur in the first 6 patients within 30 days of therapy, we proceed with additional accrual with this regimen to complete a total of 42 patients. If  $\geq 3$  toxicity events occur among the first 6 patients, we will suspend the study pending data review.

*Toxicity Event:*  $\geq$  grade 3 adverse event (CTCAE v 4.0) with an attribution of possible, probable, or definite.

### 15.4 Early Stopping Guidelines:

This study will monitor site-specific grade 4/5 toxicity. If it becomes evident that the proportion of grade 4/5 toxicity at specific sites convincingly exceeds 20%, the study will be halted for a safety consultation. Specifically, we will apply a Bayesian toxicity monitoring rule that suspends the enrollment if the posterior probability of toxicity being larger than 20% threshold is 75% or higher. The monitoring rule uses Beta (0.5, 5.5) as prior distribution. This means that our prior guess of the proportion of toxicity is 8.3%, and there is 90% chance that this proportion is 0.04%-30.6%. The monitoring will start from the 7th patient, and the decision rule for safety stopping is as follows:

Stop if:

# grade 4/5 toxicities $\geq$	4	5	6	7	8	9	10
Out of # patients	7 - 10	11 - 14	15 - 18	19 - 23	24 - 27	28 - 32	33 - 36
# grade 4/5 toxicities $\geq$	11	12					
Out of # patients	37 - 41	42					

The operating characteristics of the stopping rule are shown below and are based on 5000 simulations:

True AE rate	% simulated trials declaring unsafe	Average sample size (out of 42)
0.10	2.1	41.4
0.15	11.3	39.2
0.2	32.7	34.3
0.25	59.5	27.7
0.3	81.9	21.2
0.35	93.6	16.1
0.4	98.3	12.7

### 15.5 Analysis of Primary Objective

The primary efficacy analysis will estimate 6-month freedom from local. Freedom from local progression (FFLP) is defined as the elapsed time from the start date of treatment to the date of documented local. Patients who die without local progression will be censored at the time of death. We will plot the Kaplan-Meier curve for FFLP and estimate 6-month FFLP and its 95% confidence interval based on KM estimate and Greenwood's formula. The analysis population includes all registered subjects who have received at least one fraction of SBRT. Patients that develop distant metastasis before local progression will remain on study.

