### 6.3 Follow-Up Procedures

Subsequent to SBRT, patients will be followed clinically for toxicity and interval history at Months 1, 2, 3, 6, 12, and every 6 months thereafter until 3 years post SBRT. A detailed medical and physical examination will be performed at 4 weeks, 3 months, 6 months and 1 year post SBRT. The following procedures are optional at Months 1, 3, 6 and every 6 months through 3 years post SBRT:

- A complete blood count (CBC) and comprehensive chemistry panel
- CT scan or MRI including the treated site (Note: this is required at Months 3 and 6 for the reason noted below)
- Physical Exam and ECOG Performance Status

PET-CT will be recommended at 3 months, 6 months, and annually thereafter however all are optional.

CT scans at 3 and 6 months will be used to determine radiographic response based on RECIST 1.1 criteria.

All follow-ups may be conducted by telephone for patient convenience. Study staff will request any of the optional procedures noted above that were performed by local physicians to be forwarded for study records.

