### 6.4 Duration of Therapy

The patient will initiate Nelfinavir oral therapy twice daily seven days prior to SBRT. Within three weeks of the initial treatment planning imaging study, SBRT will be administered in a single dose to each treated lesion. After completion of SBRT a second seven day cycle of Nelfinavir will occur.

If scheduling or safety prevents all lesions from being irradiated within one day, participants will complete Cycle #2 of Nelfinavir then undergo a minimum of 7 days “clear out”. Following this break participants will repeat Cycle #1 of Nelfinavir then receive radiation to the remaining lesions followed by a repeat Cycle #2 of Nelfinavir. This process

may not exceed three “rounds” of treatment (NFV1, SBRT, NFV2) and may include repeat imaging and/or blood work..

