### 10. STUDY CALENDAR

Parameter	Pre-Study	NFV^ Cycle #1	SBRT ~	NFV^ Cycle #2	Follow-Up%								
					1M (+/- 5 days)	2M (+/- 7 days)	3M i (+/- 7 days)	6M @, h, i	12M @,i	18M @,i	24M @,i	30M @,i	36M @,i
Informed Consent	X												
Demographics	X												
Med HX & Medication Rev	X				X		X	X	X	X	X	X	X
Physical Exam	X				X		X	X	X	X	X	X	X
Vital Signs	X				X								
Height	X				X								
Weight	X				X								
Perf Status	X		X		X	X	X	X	X	X	X	X	X
CBC w/ Diff a	X f				X		X	X	X	X	X	X	X
Serum Chem b	X f				X		X	X	X	X	X	X	X
Coagulation Profile	X f												
Blood Draw for Phospho-Akt	X f		X		X*								
CT or MRI h (of Involved Site(s) o )	X f				X		X	X	X	X	X	X	X
PET-CT*	X f						X	X		X		X	
CT-Guided Fiducial Placement*	X												
AE Evaluation g	X	X d		X d	X	X	X	X	X	X	X	X	X
B-HCG e	X												

^ Nelfinavir (NFV): to be administered in two cycles (1250 mg BID (orally) for 7 days/cycle). Cycle #1 will conclude the day prior to SBRT. Cycle #2 will initiate the day after completion of SBRT.  
~ SBRT: to be administered in one day. However, if scheduling or safety prevents all lesions from being irradiated within one day, participants will complete Cycle #2 of Nelfinavir then undergo a minimum of 7 days “clear out”. Following this break participants will repeat Cycle #1 of Nelfinavir then receive radiation to the remaining lesions followed by a repeat Cycle #2 of Nelfinavir. This process may not exceed three “rounds” of treatment (NFV1, SBRT, NFV2) and may include repeat imaging and/or blood work. Accordingly, the study calendar will be affected.  
% Follow-up appointments will be scheduled based on date of SBRT completion.  
\* indicates optional  
@ +/- 30 days  
a. Including platelets.  
b. Albumin, Alkaline Phosphatase, Total Bilirubin, Bicarbonate, BUN, Calcium, Chloride, Creatinine, Glucose, Potassium, Total Protein, SGOT [AST], SPGT [ALT], Sodium.  
c. Tumor measurements are to be calculated after all radiographic tests.  
d. Will occur on the last day of Nelfinavir Cycle #1 or on date of SBRT administration and the last day of Nelfinavir Cycle #2. May be conducted via phone.  

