e. Serum pregnancy test (women of childbearing potential).  
f. Should occur within 30 days of start of Nelfinavir.

SBRT and Nelfinavir

Protocol Chair: [name]

J12137 (NA\_00069585) - May 19, 2020

g. Follow up AE evaluations may be conducted via phone.
h. Required at 3 and 6 months
i. May be conducted via telephone. All procedures are optional, EXCEPT for interval history and AE evaluations. Study staff will remind subjects of upcoming optional procedures at each telephone or follow-up visit. If obtained locally, staff will request that the results be forwarded for study records.

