#### 11.5.5 Clinical Response Parameters

**Time to Local Progression (TTLP)** is defined as the elapsed time from the start of treatment to the date of documented local progression or death, whichever happens earliest.

**Progression-Free Survival (PFS)** is defined as the time from starting treatment to the time of first documented tumor progression or death due to any cause, whichever occurs first. Death is considered as an event here. For subjects whose disease does not progress or who do not die, PFS will be censored at the time of the last visit.

**Time to Progression (TTP)** is defined as the time from starting treatment to the time of first documented tumor progression. Subjects who do not progress will be censored at the time of the last contact. In addition, death from any cause will also be censored.

**Overall Survival (OS)** is defined as the time from starting treatment until death due to any cause. For subjects who do not die, time to death will be censored at the time of last contact.

**Locoregional Control (LRC)** is defined as the time from starting treatment until local and/or regional relapse is documented

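### Section 15.5 reads FFLP at 6 months, but the deciding scan may be dated up to 30 days later and no rule counts it, so late scans can only raise the primary estimate

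*Combined protocol and SAP*

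**What the plan says.** - **Primary endpoint (15.5).** "Freedom from local progression (FFLP) is defined as the elapsed time from the start date of treatment to the date of documented local". The estimate is the Kaplan-Meier value at 6 months with a Greenwood 95% interval. Patients who die without local progression are censored at death. No other censoring rule is given for FFLP.
- **The related definition (11.5.5).** TTLP is "the elapsed time from the start of treatment to the date of documented local progression or death". It uses the same starting phrase, again undefined.
- **When treatment starts (6.4 and 10).** "The patient will initiate Nelfinavir oral therapy twice daily seven days prior to SBRT", and in the calendar "Cycle #1 will conclude the day prior to SBRT. Cycle #2 will initiate the day after completion of SBRT". First nelfinavir and SBRT are therefore 7 days apart in a one-round patient.
- **When scans happen (6.3 and 10).** "Follow-up appointments will be scheduled based on date of SBRT completion". The 3M window is ±7 days and the 6M window is ±30 days. Imaging is "Required at 3 and 6 months", and "CT scans at 3 and 6 months will be used to determine radiographic response based on RECIST 1.1 criteria". Other follow-up imaging is optional.
- **Multi-round treatment (10).** If not all lesions can be irradiated in one day, "participants will complete Cycle #2 of Nelfinavir then undergo a minimum of 7 days" without drug before the next round, up to three rounds.
- **Competing schedule (11.1).** Response is re-evaluated at 4, 12 and 24 weeks after treatment.
- **Benchmarks (15.2).** A 6-month FFLP of 70% or less is insufficient, and 90% is the level that would warrant further study.

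**The concern.** The event is dated at documentation, the curve is read at a fixed time, and that time falls in the middle of the 60-day window for the scan that decides the result. A patient who progresses between the 3M and 6M scans normally has that shown only by the 6M scan. If the scan is dated before the read-off, the patient is an event. If it is dated after, the same patient is counted as progression-free. No section says that a 6M-window scan belongs to the 6-month result.

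Progressions documented by 6 months are a subset of those that have occurred by 6 months, so late documentation works in one direction. The shift is larger when more patients progress, which means it is larger for an inactive regimen than for an active one. In a single-arm trial judged against fixed benchmarks, that is the less comfortable direction.

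**Working it through.** **Planning values.** The plan gives no figure for this shift, so I first checked the benchmarks it would act on. The one-sample normal formula gives [(1.96·√(0.7·0.3) + 1.2816·√(0.9·0.1))/0.2]² = 41.1, so 42 patients, with 90.8% power. This reproduces the stated size before any allowance for dropout, which is a separate matter. The hazards in 15.2 also reproduce: −ln(0.70)/6 = 0.059 and −ln(0.90)/6 = 0.018 per month. Constant hazard is therefore the plan's own working model, and I use it below.

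**Set-up.** Day 183 is 6 months. Let s be the true 6-month FFLP and S(t) = s^(t/183). The 3M scan is on day 91 from SBRT and the 6M target is day 183 from SBRT. Assumptions: one round, the 3M scan on time, no other scans and no censoring. A patient contributes S(6M scan date) if that date is on or before day 183, and otherwise S(3M scan date).

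**What rests on the 6M scan.** At s = 0.70, S(91) = 83.7%. The share of 6-month progressions arising after the 3M scan is (0.837 − 0.700)/0.300, about 46%. At s = 0.90, S(91) = 94.9% and the share is 49%.

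**SBRT as time zero**
- Every scan on date: 70.0% and 90.0%, no shift.
- Every 6M scan late in the window: 83.7% and 94.9%, so about +14 and +5. This is the top of the range.
- Scans even over days 153–213: half are on time. The mean of S over days 153–183 is 72.1% (90.8% at s = 0.90). The read-off is ½·72.1 + ½·83.7 = 77.9%, and ½·90.8 + ½·94.9 = 92.8%. The shifts are about +8 and +3.
- The same spread, with progression-free patients censored at their last scan (simulation): about 76% and 92%, so about +6 and +2.

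**First nelfinavir as time zero.** All visits move 7 days later: 3M to day 98, the 6M target to day 190, the 6M window to days 160–220.
- Scans even over the window: 23/60 = 38% fall by day 183, and their mean S is 71.6%. S(98) = 82.6%. The read-off is 0.383·71.6 + 0.617·82.6 = 78.4%, against 77.9% on the SBRT clock. At s = 0.90 it is 93.0%, against 92.8%.
- Every scan on date (day 190): all miss the read-off, so the estimate is S(98) = 82.6%, or 94.5% at s = 0.90.

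**Multi-round patients.** At the calendar's minimum spacing (7 drug days, SBRT, 7 drug days, 7 days off), SBRT falls on days 7, 29 and 51 from first nelfinavir. With three rounds the 6M window is days 204–264 from first nelfinavir, or 197–257 from first SBRT, wholly after day 183 on either clock. The 3M scan also moves later, so the read-off is S(142) = 75.8% or S(135) = 76.9%, about +6 to +7. For two rounds it is 79.0% or 78.9%, about +9.

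**Section 11.1 timing.** Week 24 is day 168 from SBRT or day 175 from first nelfinavir. On date, a true 70% reads 72.1% or 71.1%. If the calendar's ±30 days is also applied, which is an assumption, it reads 76.1% or 76.7%.

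**The case against.** **The protocol dates progression at documentation.** This is usual practice, and the shift is measured against an onset time the plan does not claim to observe. A 70% benchmark that was itself scan-dated would share part of it. Both points are fair. The benchmark's source is not stated, however, and the convention does not explain why two patients with the same finding at the same scheduled visit should count differently.

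**The size is not known.** This stands. Scans exactly on date with SBRT as time zero give no shift, and scans early in the window give only about +2 and +1. An optional extra scan near 4.5 months would reduce the evenly spread case at a true 70% to about +4.

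**Censoring matters.** It does, and 15.5 covers only deaths. The upward direction is a property of late dating. Suppose progression-free patients were censored at their last scan and nearly all 6M scans came before the read-off. The shrinking risk set could then pull the estimate down. That would be a different fault, and the plan states no such rule.

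**Other sections may cover it.** Per-lesion local control at 6 months (15.6) is a partial cross-check, but it is secondary and does not change 15.5. The 24-week wording in 11.1 would shrink the shift if scans kept to it, but it conflicts with the calendar and carries no window.

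**Stronger readings the documents do not support**
- That the estimate is inflated by 8 points. This is one scenario among several.
- That the undefined start date is the main driver. With scans spread over the window it adds about 0.5 point at a true 70%.
- That extra rounds enlarge the shift. They widen the gap between the clocks, but three rounds give a smaller shift than one, and the number of such patients is not given.
- That the false-positive rate is known. If one assumes 36 evaluable patients and success when the Greenwood lower limit exceeds 70% (30/36 or more), the chance of success at a true 70% goes from about 5% to 29% with evenly spread scans. The protocol states no decision rule, so this is illustration only.

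**Conclusion.** The point holds. As written, 15.5 counts a progression first seen on a late 6M-window scan as progression-free at 6 months, and late documentation can only raise the primary estimate. Under constant hazard, one round and no scans other than 3M and 6M, the shift is 0 to about +14 points at a true 70% and 0 to about +5 at a true 90%. Evenly spread scans give about +8 and +3, or about +6 and +2 with last-scan censoring and SBRT as time zero. A different hazard shape would move these figures. Confidence is high in the text and the direction, but not in any single size.

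The undefined time zero is secondary. It becomes decisive only if scans cluster on the nominal 6M date, where the choice of clock separates about 70% from 83% at a true 70%.

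This should be fixed before the primary analysis. Choosing the clock or the read-off after seeing the data would be an unblinded choice.

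**What to change.** In 15.5:

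1. Name the date that is time zero for FFLP. Say how multi-round patients are handled, including a local progression found before the last round.
2. Count every 6M-window scan towards 6-month FFLP by assigning its finding, progression or none, to the scheduled 6M visit. State how progression-free patients are otherwise censored. Add an interval-censored (Turnbull) estimate at 6 months as a sensitivity analysis.
3. Reconcile the 12- and 24-week wording in 11.1 with the study calendar. This alone does not remove the shift.

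**Cost.** Wording only, with no new scans or patients. The reported FFLP may be less favourable. With evenly spread scans, visit assignment returns a true 70% to about 70% with SBRT as time zero. It is slightly conservative from first nelfinavir (about 69%). It is more so for multi-round patients if time zero precedes SBRT completion: about 66–67% for two rounds and 63–64% for three. The interval-censored estimate uses the actual scan dates and shows how much this matters.

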### **15.2 Sample Size/Accrual Rate**

The primary endpoint will be freedom from local progression at 6 months. The treatment regimen would be considered of insufficient activity for further study in this population

if the 6-month FFLP rate is 70% or less, and the minimum required level of efficacy that would warrant further study with the proposed regimen is a 90% FFLP at 6 months. The accrual rate is 3 patients per month, and the patients will be followed for up to 3 years. A total of 42 patients will be entered in the study accounting for a 15% dropout rate. This study would have 90% power to detect an improved 6-month FFLP from 70% to 90% using a two-sided test at significance level 0.05. Alternatively, this corresponds to the power to detect a reduction of hazard rate from 0.06 to 0.02, a reduction of 70% in hazard rate.

There will be no interim analysis for futility, since the progression endpoint will not have been reached by a meaningful number of patients before full accrual.

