## **15.8 Evaluation of Response**

All patients included in the study must be assessed for response to treatment, even if there are major protocol treatment deviations or if they are ineligible. Each patient will be assigned one of the following categories: 1) complete response, 2) partial response, 3) stable disease, 4) progressive disease, 5) early death from malignant disease, 6) early death from toxicity, 7) early death because of other cause, or 9) unknown (not assessable, insufficient data). [Note: By arbitrary convention, category 9 usually designates the “unknown” status of any type of data in a clinical database.]

All of the patients who met the eligibility criteria (with the possible exception of those who received no study medication) should be included in the main analysis of the response rate. Patients in response categories 4-9 should be considered to have a treatment failure (disease progression).

All conclusions should be based on all eligible patients. Sub-analyses may then be performed on the basis of a subset of patients, excluding those for whom major protocol deviations have been identified (e.g., early death due to other reasons, early discontinuation of treatment, major protocol violations, etc.). However, these sub-analyses may not serve as the basis for drawing conclusions concerning treatment efficacy, and the reasons for excluding patients from the analysis should be clearly reported. The reason for performing subset analyses would be to generate hypotheses for future prospective clinical trials.

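### FFLP is censored at death whatever the date of the last scan, with no rule for living patients, so patients without a 6-month scan could be counted as locally controlled at 6 months

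*Combined protocol and SAP*

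**What the plan says.** Section 15.2 sets the endpoint: "The primary endpoint will be freedom from local progression at 6 months". The regimen is judged insufficient "if the 6-month FFLP rate is 70% or less", and the level that would warrant further study "is a 90% FFLP at 6 months".

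Section 15.5 times FFLP from the start of treatment to documented local progression and estimates it by Kaplan-Meier with Greenwood's variance. It gives one censoring rule: "Patients who die without local progression will be censored at the time of death". It gives no date for patients who are alive without local progression, and no rule for a missing 6-month scan.

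Other endpoints have their own rules, and these differ:
- TTP (11.5.5): "Subjects who do not progress will be censored at the time of the last contact".
- PFS: last visit in 11.5.5, but last evaluation in 15.1.2 for patients lost to follow-up.
- Response rate (15.8): unknown status counts as failure.

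On imaging, section 6.3 and calendar footnote h require CT or MRI at months 3 and 6. Calendar footnote i, attached to the visits from month 3 on, makes every procedure optional apart from interval history and adverse event evaluation. Section 6.3 adds: "All follow-ups may be conducted by telephone for patient convenience".

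**The concern.** After the last scan, a patient's local status is unknown. A censoring date later than that scan keeps the patient in the risk set for a period in which an event could not have been documented.

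Take a patient scanned at month 3, not scanned again, who dies at month 10. Under 15.5 this patient is censored at month 10, so counts in the month-6 denominator as progression-free. The same would happen to a living patient reached only by telephone, if the analyst filled the gap in 15.5 with the TTP rule.

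With scans missing at random the error is upward, and it acts directly on the figure compared with 70%. Because the rule for living patients is unwritten, it could also be chosen after the data are seen.

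**Working it through.** **Inputs from the documents.** 6-month FFLP 70% (null) and 90% (alternative), section 15.2; scans at months 3 and 6, section 6.3; Kaplan-Meier and the death rule, section 15.5; follow-up to 3 years, sections 6.3 and 15.2.

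**Assumptions not in the documents.** A share u of patients alive at month 6 has no 6-month scan (15% and 30% used). Hazard is constant, visits fall on nominal dates, scans are missing at random, the month-3 scan is done, and there are no later scans unless stated.

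**Plan's own figure.** Monthly hazard at 70%: -ln(0.70)/6 = 0.0594. At 90%: -ln(0.90)/6 = 0.0176. Section 15.2 gives 0.06 and 0.02, so the constant-hazard model matches the plan.

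**Expected estimate.** At a true 70%, FFLP at month 3 is S3 = √0.70 = 0.8367, and the chance of progression in each 3-month interval is q = 1 - 0.8367 = 0.1633. Let g be the fraction of the unscanned patients kept at risk through month 6. Then

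expected 6-month KM = S3 × [1 - q(1 - u) / ((1 - u) + g·u)].

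1. *Censoring at last scan, g = 0:* 0.8367 × (1 - 0.1633) = 70.0% for any u.

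2. *All unscanned patients carried past month 6, g = 1:*
   - u = 15%: 0.8367 × (1 - 0.1633 × 0.85) = 72.0%.
   - u = 30%: 0.8367 × (1 - 0.1633 × 0.70) = 74.1%.
   - The excess is u × S3 × q = u × 13.7 points.

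3. *Death rule alone:* unscanned patients who die between months 6 and 36 are kept, and those still alive are censored at their last scan. With an assumed median survival of 24 months, independent of local progression, g = 1 - 2^(-30/24) = 0.58.
   - u = 15%: 0.8367 × [1 - 0.1633 × 0.85/(0.85 + 0.087)] = 71.3%.
   - u = 30%: 0.8367 × [1 - 0.1633 × 0.70/(0.70 + 0.174)] = 72.7%.
   - A simulation under the same assumptions gave 71.2% to 72.7%.

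4. *Deaths before month 6, all scans otherwise done:* these patients leave the risk set before the month-6 scan under either rule. Simulation with 0% to 30% early deaths gave identical estimates under both rules (about 70.0% and 90.0%).

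5. *Month-3 scan also missed, all carried past month 6:* 0.70 + 0.30u, that is 74.5% at u = 15% and 79.0% at u = 30%.

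6. *Later scans obtained, u = 30%:* if half of the unscanned patients have a month-12 scan, last-scan censoring gives 72.4% (g = 0.5), against 74.1% when all are carried. If all have one, the two rules agree at about 74%.

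7. *At a true 90%:* S3 = 0.9487 and q = 0.0513, so the excess with all carried is u × 4.9 points: 0.7 at u = 15% and 1.5 at u = 30%.

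**Effect on a decision (illustration).** Take success as a plain Greenwood lower 95% limit above 70%, with 42 patients, 10% dying before month 6 and a true FFLP of 70%. Carrying all unscanned patients past month 6 gives false success of 8.7% (u = 15%) and 13.1% (u = 30%), against 5.3% and 5.9% with last-scan censoring (6,000 simulated trials).

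**The case against.** The strongest reply is that the scans are required. Section 6.3 and footnote h both say so for months 3 and 6, and if every patient is scanned the rules give the same answer. This limits the size but does not close the gap: footnote i, attached to the same visits, says the opposite, and the plan has no rule for a missed scan.

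A reader might infer that FFLP is censored at last contact. The documents do not say that. The last-contact rule is written for TTP, and 15.1.2 uses last evaluation for PFS. For living patients the FFLP rule is missing, not wrong.

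A reader might also infer that the death rule makes every patient who dies look controlled at 6 months. It does not: deaths before month 6 cause no bias when the month-3 scan was done (item 4).

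Three further limits stand. The missed-scan share is assumed. Section 15.5 does not name the type of interval or a success rule, so the false-success figures are illustrations; with a log-log interval the baseline is lower, about 1-2%. And last-scan censoring is not a full cure when a missed 6-month scan is followed by a later one, because progression found then is dated after month 6 (item 6).

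Section 15.8 does not contradict 15.5. Its treatment of unknowns governs the response rate, a different endpoint.

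**Conclusion.** The point holds in a limited form. Section 15.5 ties FFLP censoring to death and not to imaging, and leaves living patients without a rule, so the 6-month estimate could be inflated.

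At a true 70%, with 15-30% lacking a 6-month scan and the assumptions above, the size is about 2 to 4 points if all such patients are carried past month 6, and about 1 to 3 points from the written death rule alone. It is larger if the month-3 scan is also missed. The part due to the censoring rule shrinks if later scans are obtained. At a true 90% it is about 0.7 to 1.5 points with all carried.

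The documents do not support saying that the estimate is inflated as a fact: that depends on how many 6-month scans are missed and on a rule not yet written. This is a cheap improvement to the primary analysis, not a flaw that invalidates it.

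**What to change.** In 15.5, replace the death sentence with a rule covering everyone: patients without documented local progression, alive or dead, are censored at the last CT or MRI that images all treated lesions, or at the start date if there is no post-treatment scan. State that telephone contact and date of death do not extend local follow-up.

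Report how many patients are censored before the 6-month scan, and add one sensitivity analysis that counts them as failures. Reconcile calendar footnotes h and i with each other and with section 6.3.

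The cost is a short rule, one count, one sensitivity line and a footnote correction. The downside is fewer patients at risk at month 6, so a slightly less favourable estimate and lower precision. In the illustration above, at a true 90% and u = 15%, the chance that the lower limit exceeds 70% is 92.3% with last-scan censoring, against 96.0% with all carried and 93.9% with every scan done.
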